2.4.4.3 Deaths

Listing of all Deaths (Screened participants) will be generated.

2.4.4.4 Analyses of vital sign variables

The incidence of PCSAs at any time during the whole on-treatment period will be summarized only for heart rate by treatment group irrespective of the Baseline level and/or according to the following Baseline status categories:

- Normal/missing
- Abnormal according to PCSA criterion or criteria

2.5 DATA HANDLING CONVENTIONS

2.5.1 General conventions

The following formulas will be used for computation of parameters.

Demographic formulas

The participant's duration of diabetes (years) is calculated using the date of informed consent and the date of diabetes diagnosis.

If date of diabetes diagnosis is a complete date, then the duration of diabetes is (date of informed consent - date of diabetes diagnosis + 1) / 365.25. If date of diabetes diagnosis is a partial date:

- a) year and month are not missing, but day is missing, then day = 01
- b) year is not missing, but month and date are both missing, then month is imputed to January and the day = 01.

Renal function formulas

eGFR will be calculated using the 4-variable Modification of Diet in Renal Disease (MDRD-4) formula below (1):

- $$\text{eGFR (mL/min/1.73 m}^2\text{)} = 175 \times \text{serum creatinine (mg/dL)}^{1.154} \times \text{Age(year)}^{-0.203} \times 1.212 \text{ [if black]} \times 0.742 \text{ [if female]}$$

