5.2 EXCLUSION CRITERIA

Participants are excluded from the study if any of the following criteria apply:

Medical conditions

- E 01. History of severe hypoglycemia requiring emergency room admission or hospitalization within 3 months prior to screening.
- E 02. Retinopathy or maculopathy with one of the following treatments, either recent (within 3 months prior to screening) or planned: intravitreal injections or laser or vitrectomy surgery.
- E 03. Clinically relevant history of GI disease associated with prolonged nausea and vomiting, including (but not limited to) gastroparesis, unstable and not controlled gastroesophageal reflux disease requiring medical treatment within 6 months prior to screening or history of surgery affecting gastric emptying.
- E 04. History of pancreatitis (unless pancreatitis was related to gallstones and cholecystectomy has been performed), pancreatitis during previous treatment with incretin therapies, chronic pancreatitis, pancreatectomy.
- E 05. Personal or family history of MTC or genetic conditions that predisposes to MTC (eg, multiple endocrine neoplasia syndromes).
- E 06. Body weight change of ≥ 5 kg within the last 3 months prior to screening.
- E 07. Systolic blood pressure >180 mmHg and/or diastolic blood pressure >100 mmHg at randomization.
- E 08. End-stage renal disease as defined by estimated glomerular filtration rate (eGFR, by Modification of Diet in Renal Disease [MDRD]) of <15 mL/min/1.73 m².
- E 09. Laboratory findings at the Screening Visit:
 - ALT or aspartate aminotransferase (AST) $>3 \times$ ULN or total bilirubin $>1.5 \times$ ULN (except in case of documented Gilbert's syndrome).
 - Amylase and/or lipase: $>3 \times$ ULN.
 - Calcitonin ≥ 5.9 pmol/L (20 pg/mL).
- E 10. Known presence of factors that interfere with the HbA1c measurement (eg, specific hemoglobin variants, hemolytic anemia) compromising the reliability of HbA1c assessment or medical conditions that affect interpretation of HbA1c results (eg, blood transfusion or severe blood loss in the last 3 months prior to randomization, any condition that shortens erythrocyte survival).

E 11. Any clinically significant abnormality identified either in medical history or during screening evaluation (eg, physical examination, laboratory tests, ECG, vital signs) or any AE during screening period which, in the judgment of the Investigator, would preclude safe participation in the study or constrains efficacy assessment.

Prior/concomitant therapy

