- Antidiabetic drugs at the time of screening (basal insulin, basal insulin + SU, basal insulin + OAD other than SU);
- Basal insulin dose at Screening (U, U/kg);
- Basal insulin dose at Baseline (U, U/kg);
- Duration of treatment with (any) basal insulin;
- Estimated Glomerular Filtration Rate (eGFR) at baseline (ml/min/1.73m²);
- Estimated glomerular filtration rate (eGFR) categories at baseline (<15 ml/min/1.73 m² [End stage renal Disease], \geq 15 to $<$ 30 ml/min/1.73 m² [Severe decrease in glomerular filtration rate (GFR)], \geq 30 to $<$ 60 ml/min/1.73 m² [Moderate decrease in GFR], \geq 60 to $<$ 90 ml/min/1.73 m² [Mild decrease in GFR], and \geq 90 ml/min/1.73 m² [Normal])

Any technical details related to computation, dates, and imputation for missing dates are described in [Section 2.5](#).

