2.4 STATISTICAL METHODS

In general, descriptive statistics of quantitative efficacy and safety endpoints (result and change from baseline) by scheduled visit will be provided on observed cases (OC), ie, only including participants having a non-missing assessment at a specific visit.

Due to study early termination, the analyses specified in this document focus on demographics, disease characteristics at baseline, exposure, participants disposition, and safety. Primary and secondary efficacy data will be descriptively summarized.

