2.4.1 Demographics and baseline characteristics

Parameters described in [Section 2.1.1](#) will be summarized on the ITT population by randomized treatment group and overall using descriptive statistics.

Continuous data will be summarized using the number of available data, mean, standard deviation (SD), median, minimum, and maximum for each treatment group. Categorical and ordinal data will be summarized using the number and percentage of participants in each treatment group. Missing data will not be categorized in the summaries.

Technical formulas are described in [Section 2.5](#).

P-values on demographic and baseline characteristic data will not be calculated.

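### As the text reads, SAP 2.5.1 raises creatinine to the power +1.154, so calculated baseline eGFR would rise with creatinine, against the SAP's own category labels

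*SAP*

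**What the plan says.** SAP 2.5.1, under the renal function formulas, states that eGFR will be calculated with the four-variable MDRD formula. The constant is 175, with factors of 1.212 for black participants and 0.742 for women. The creatinine term reads "serum creatinine (mg/dL)}^{1.154" and the age term reads "Age(year)}^{-0.203"; the braces are markup for superscripts. Creatinine therefore carries a positive exponent and age a negative one.

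The formula has a stated use. SAP 2.1.1 lists baseline eGFR as a value and also "Estimated glomerular filtration rate (eGFR) categories at baseline", with labels from end-stage disease (below 15) to normal (90 or above). It then says: "Any technical details related to computation, dates, and imputation for missing dates are described in" Section 2.5. SAP 2.4.1 says the baseline parameters "will be summarized on the ITT population by randomized treatment group and overall using descriptive statistics", and adds: "Technical formulas are described in" Section 2.5. SAP 2.4 keeps this summary after early termination, since the remaining analyses "focus on demographics, disease characteristics at baseline, exposure, participants disposition, and safety".

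Protocol 5.2 (E 08) excludes "End-stage renal disease as defined by estimated glomerular filtration rate (eGFR, by Modification of Diet in Renal Disease [MDRD]) of <15" mL/min/1.73 m², so the protocol also places severe disease at the low end of the scale.

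**The concern.** With a positive exponent, calculated eGFR increases as creatinine increases. The documents say the opposite in several places and no outside source is needed to see it:

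- The category labels in SAP 2.1.1 and Appendix A make low eGFR the diseased end.
- E 08 does the same.
- SAP Appendix A sets an abnormal-high criterion for creatinine (150 µmol/L or more).
- Protocol 10.5.4 treats an acute rise in creatinine as renal dysfunction.

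If a programmer codes the line as it stands, participants with raised creatinine appear in the baseline table with normal renal function, and some with low creatinine appear impaired. The SAP is the specification against which the program is written and checked, so a faithful implementation would give the wrong table.

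**Working it through.** **Inputs.** Constant 175, creatinine exponent of magnitude 1.154, age exponent -0.203 and female factor 0.742 come from SAP 2.5.1. The categories come from SAP 2.1.1 and Appendix A: below 15 end stage, 15 to below 30 severe, 30 to below 60 moderate, 60 to below 90 mild, 90 or above normal. The creatinine threshold of 150 µmol/L comes from SAP Appendix A. Assumed for illustration: age 60 (75 where stated), no race factor, and 88.4 µmol/L per mg/dL. The SAP gives no worked eGFR value to reproduce.

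**Formula.** eGFR = K × Cr^e, where K = 175 × Age^(-0.203) × (0.742 if female). At age 60, K = 76.22 for a man and 76.22 × 0.742 = 56.56 for a woman. The two versions differ only in e = +1.154 or e = -1.154.

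**Values at age 60:**

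| Sex | Creatinine (mg/dL) | e = +1.154 (as the text reads) | e = -1.154 |
|---|---|---|---|
| Man | 0.7 | 50.5, moderate | 115.0, normal |
| Man | 1.0 | 76.2, mild | 76.2, mild |
| Man | 1.2 | 94.1, normal | 61.8, mild |
| Man | 1.5 | 121.7, normal | 47.7, moderate |
| Man | 2.0 | 169.6, normal | 34.3, moderate |
| Woman | 0.7 | 37.5, moderate | 85.4, mild |
| Woman | 1.0 | 56.6, moderate | 56.6, moderate |
| Woman | 1.5 | 90.3, normal | 35.4, moderate |
| Woman | 2.0 | 125.9, normal | 25.4, severe |

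The two signs agree exactly only at 1.0 mg/dL. Doubling creatinine multiplies the result by 2^1.154 = 2.23 where it should divide by 2.23.

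**Where the category does not change.** For a man aged 60 both versions must lie in 60 to below 90. The upper limit binds: (90/76.22)^(1/1.154) = 1.155, with reciprocal 0.866. On a 0.001 mg/dL grid the unchanged bands are:

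- man 60: 0.866 to 1.154
- woman 60: 0.951 to 1.052
- man 75: 0.846 to 1.183
- woman 75: 0.914 to 1.094

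**At the E 08 limit.** With the negative exponent, eGFR is 15 when Cr = (K/15)^(1/1.154), that is 4.09 mg/dL (man 60) or 3.16 mg/dL (woman 60). The positive exponent at that creatinine gives K × (K/15) = K²/15: 76.22²/15 = 387.3 and 56.56²/15 = 213.2, both normal. Over ages 40 to 80 and both sexes the range is 189.7 to 456.6, all normal. The positive version falls below 15 only when Cr < (15/K)^(1/1.154), that is below 0.244 (man 60) or 0.317 mg/dL (woman 60).

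**At the creatinine abnormality threshold.** 150/88.4 = 1.697 mg/dL. The positive exponent gives 140.3 (man 60) and 104.1 (woman 60), both normal; the negative gives 41.4 and 30.7, both moderate. A participant flagged for high creatinine would be tabulated with normal renal function.

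**The case against.** The strongest objection is that the point rests on one superscript minus sign in text converted from a PDF. The equation appears there as reconstructed markup, and reading damage is not an error in the plan. Recalculation shows what +1.154 implies, not that the SAP page prints it. This stands. The surviving minus on the age exponent makes a lost sign less likely but does not rule it out.

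Second, the line may never drive the table. eGFR by MDRD is also listed as a central-laboratory parameter (SAP 2.1.4.3, protocol Appendix 2), and SAP 2.1.1 defines baseline eGFR as an average of pre-dose values, which fits laboratory-reported results. The formula is also named and referenced, and a value such as 169.6 at creatinine 2.0 mg/dL would be conspicuous. Against that, SAP 2.5.1 says eGFR will be calculated, so the documents do not settle which value is used.

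Third, the examples at the E 08 limit lie at the exclusion boundary, so such participants would be rare or absent. That is fair: those figures show the direction of the error, not its frequency in this trial.

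Finally, confining the effect to the baseline table is an inference. SAP 2.4.4 has general abnormality rules for laboratory tests and Appendix A lists eGFR categories. However, the methods set out an abnormality summary only for heart rate (2.4.4.4) and contain no laboratory analysis subsection.

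**Conclusion.** The concern holds on the text as read, as a minor point with medium confidence. The positive creatinine exponent cannot be reconciled with the SAP's category labels, its high-creatinine criterion or E 08, and nothing elsewhere in the documents supplies the negative exponent. Outside a narrow band around 1.0 mg/dL the category is wrong, in either direction. How many participants fall outside that band is unknown.

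The consequence is a wrong descriptive baseline eGFR summary. It depends on two conditions: the source page really shows a positive exponent, and the calculated eGFR is tabulated in place of the laboratory's. Efficacy, eligibility, identification of acute renal failure (by a coded term query in SAP Table 1) and the creatinine abnormality criteria, which use creatinine directly, are not affected.

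**What to change.** Check the sign of the creatinine exponent on the source page of SAP 2.5.1. If the minus sign is there, no change is needed. If the exponent is positive, change it to -1.154 and confirm that the derivation program, and any baseline eGFR table already produced, use the negative exponent. Optionally, SAP 2.1.1 could also say whether the laboratory-reported or the calculated eGFR is tabulated. The cost is one character in the SAP and one check of the program.

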2.5.2 Data handling conventions for secondary efficacy variables

No special data handling.

2.5.3 Missing data

For categorical variables, participants with missing data are not included in calculations of percentages unless otherwise specified. When relevant, the number of participants with missing data is presented.

Derived variables will be considered missing if any of the original variables required to calculate them are missing. For example, if either a baseline assessment or an endpoint assessment is missing for a particular participant, then change from baseline at endpoint will be missing. Depending upon the assessment, analyses may not include all participants in the analysis population, because certain participants in the intended population may have missing data.

Handling of computation of treatment duration if investigational medicinal product end of treatment date is missing

For the calculation of the treatment duration, the date of the last dose of IMP is equal to the date of last administration reported on the treatment status case report form page. If this date is missing, the exposure duration should be left as missing.

In the definition of the whole on-treatment period, the date of the last dose of IMP is equal to the date of the last administration reported on the treatment status case report form page. If this date is missing, the date of the last IMP injection in the exposure page will be used for participants with at least 1 injection or the date of visit 2/randomization visit will be used for participants who were lost to follow-up after the initial dispensation of IMP.

Handling of medication missing/partial dates

No imputation of medication start/end dates or times will be performed. If a medication date or time is missing or partially missing and it cannot be determined whether it was taken prior or concomitantly, it will be considered a prior, concomitant, and posttreatment medication.

Handling of adverse events/hypoglycemia with missing or partial date/time of onset

Missing or partial AE/hypoglycemia onset dates and times will be imputed so that if the partial AE/hypoglycemia onset date/time information does not indicate that the AE/hypoglycemia started prior to treatment or after the whole on-treatment period, the AE/hypoglycemia will be classified as treatment-emergent. No imputation of AE end dates/times will be performed. These data imputations are for categorization purpose only and will not be used in listings. No imputation is planned for date/time of AE resolution.

Handling of adverse events/hypoglycemia when date and time of first investigational medicinal product administration is missing

When the date and time of the first IMP administration is missing, all AEs/hypoglycemia that occurred on or after the day of randomization should be considered as TEAEs. The exposure duration should be kept as missing.

Handling of potentially clinically significant abnormalities

If baseline is missing, the participant will be grouped in the category “normal/missing at Baseline.”

For PCSAs with 2 conditions, one based on a change from Baseline value or a normal range and the other on a threshold value, with the first condition being missing, the PCSA will be based only on the second condition.

Handling of missing screening value to derive randomization strata

In case of missing data at screening visit for HbA1c, unscheduled data before randomization visit can be used. If the sample is confirmed as being for the purpose of a re-screen, then the result is sent to be integrated into IRT. In case of several data collected, the earliest is used.

Participants who do not have a documented stable daily dose of SU for at least 3 months prior to screening will be considered non-SU users.

Linked adverse events that worsened or became serious

An AE that worsened or became serious will have a separate record in the data from the original event record with a reference identification number that links the new record to the original record. An AE that worsened or became serious will be considered a new recurring AE in the summary of recurrent events or in the summary of events by time intervals.

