A hierarchical procedure will be performed to adjust for the multiplicity of comparison. First, the highest dose of efpeglenatide (6 mg) will be compared to placebo. If the superiority is demonstrated for the 6 mg dose of efpeglenatide, then the superiority of the 4 mg dose of efpeglenatide versus placebo will be tested. If superiority is also demonstrated for the 4 mg dose of efpeglenatide, then the lowest dose (2 mg) versus placebo will be tested. When the superiority is not obtained in a step, then the sequential testing procedure will be stopped.

Summary statistics (for screening value, baseline value, observed values, and observed changes from baseline) at scheduled visits will be provided for each treatment group over the whole treatment period including the 26-week Treatment Extension Period. The summary will include the number of observations, mean, standard deviation (SD), standard error (SE), minimum, median, and maximum. Graphical presentations will also be used to examine trends over time using mean values (\pm SE) and mean changes from baseline (\pm SE) at each of the scheduled visits (using observed cases [OC]).

- Analysis of secondary and other efficacy endpoints:**

Continuous secondary efficacy endpoints will be analyzed using the same ANCOVA model with missing values imputed by MI method as the method used for the primary efficacy endpoint analysis. Differences between treatment groups and CIs will be estimated by this method. Categorical efficacy endpoints will be analyzed by the Cochran Mantel-Haenszel method stratified by the randomization strata. For the HbA1c $<7.0\%$ analysis, participants with missing HbA1c data at Week 30 or Week 56 will be considered nonresponders in the intent-to-treat (ITT) population.

[figure not shown]
Comparisons of time-to-event endpoints between treatment groups will be performed using the Cox proportional hazards regression model with the treatment groups (efpeglenatide 2, 4, or 6 mg, or placebo), randomization stratum of screening HbA1c ($<8\%$, $\geq 8\%$), randomization stratum of SU use (yes/no), and geographical region as the factors.

Data Monitoring Committee: Yes

See Appendix 1 ([Section 10.1](#)) for details.

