
| Endpoint | Statistical Analysis Methods |
|---|---|
| | 
 Baseline BMI (<30 kg/m², ≥30 kg/m²). Diabetes duration (<10 years, ≥10 years). Country. United States/non-United States. Antidiabetic drugs at the time of screening (Lantus, Lantus + OAD). SU use at screening (Yes, No). 
The treatment effects (efpeglenatide 2, 4, or 6 mg versus placebo) across the subgroups defined for each of these factors will be estimated for the change from baseline to Week 30 in HbA1c in the ITT population and using a similar approach as applied to the analysis for the primary efficacy endpoint. The ANCOVA model will include treatment groups (efpeglenatide 2, 4, or 6 mg, placebo) and randomization stratum of screening HbA1c (<8%, ≥8%), randomization stratum of SU use (Yes, No), subgroup factor, treatment-by-subgroup factor, and region as fixed factors and using the baseline HbA1c value as a covariate. The adjusted estimates of treatment mean differences (each efpeglenatide dose versus placebo) with SE and 95% CIs will be provided across the subgroups, as appropriate. A graphical presentation of the results (ie, forest plot) will also be provided.
 
In the case that the subgroup factor is identical or similar to a randomization strata factor (eg, baseline HbA1c, SU use), only the subgroup factor (as a single factor or an interaction term) will be included in the model in order to avoid the issue of collinearity in the analysis. The corresponding strata factor will not be included in the model. In case that the subgroup factor is country, the region will not be included in the model.
 |
| Secondary | |
| Change from baseline to Week 56 in HbA1c | Continuous secondary efficacy endpoints will be analyzed using the same ANCOVA model with missing values imputed by MI method as the method used for the primary efficacy endpoint analysis. Differences between treatment groups and CIs will be estimated by this method. |
| Change from baseline to Week 30 in FPG | Categorical efficacy endpoints will be analyzed by the Cochran Mantel-Haenszel method stratified by the randomization strata. For the HbA1c <7.0% analysis, participants with missing HbA1c data at Week 30 or Week 56 will be considered nonresponders in the ITT population. |

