2.3.1 Efficacy populations

The efficacy analysis population will be the ITT population.

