2.4.3 Analyses of efficacy endpoints

Efficacy analyses will be performed on the ITT population using efficacy assessment collected during the study, including those obtained after IMP discontinuation or introduction of rescue therapy, unless otherwise specified (see [Section 2.5.4](#)).

Descriptive summary will be provided at screening, baseline, Week 30 and Week 56 displaying observed value and change from baseline for efficacy endpoints (HbA1c, FPG, body weight and % participants achieving 7%).

In summary by visits, Week 56 data will be presented respectively:

1. Including all Week 56 visits performed per protocol as well as premature end of treatment/study visit recorded as Week 56 due to early termination.
2. Including Week 56 visits for participants who completed treatment and/or study.

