2.5.4 Windows for time points

Nominal post-baseline visits will be used for descriptive statistics and time course plots.

Efficacy data at Week 30 / Week 56

The scheduled measurements at the endpoint visit (Week 30 or Week 56) as collected will be used in the efficacy analyses including those obtained after IMP discontinuation and/or introduction of rescue therapy. For participants whose efficacy measurement is not available at the endpoint visit, the measurement at unscheduled visit (including the end of treatment and/or study visit for those prematurely discontinued) will be used if the unscheduled measurement is within +/-30 days (7 days for FPG) of the date of the endpoint visit [targeted study Day 210 for Week 30 (or Day 392 for Week 56)]. If multiple measurements are associated to the same targeted date, the closest to the targeted study day will be used. In case of equality, the last measurement will be used. If there are still no measurement for a given parameter at an endpoint visit, the data is considered missing for efficacy analyses.

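### Does the SAP need correcting because its HbA1c <7% percentage leaves out participants without a value, when the protocol counted them as nonresponders?

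*SAP*

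**What the plan says.** Protocol section 9.4.1 (Table 6) sets a rule for the responder endpoint: "participants with missing HbA1c data at Week 30 or Week 56 will be considered nonresponders in the ITT population". The synopsis repeats it. In both places the rule comes directly after the stratified Cochran-Mantel-Haenszel comparison that it was meant to serve.

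The SAP was written after the early termination. Section 2.1.3.2 keeps the count of participants with HbA1c below 7.0% at Weeks 30 and 56. Section 2.4.3 lists the corresponding percentage among the efficacy summaries. On the population, section 2.3.1 says: "The efficacy analysis population will be the ITT population". Section 2.5.4 defines when a value is absent: "If there are still no measurement for a given parameter at an endpoint visit, the data is considered missing for efficacy analyses". Section 2.5.3 then gives the default: "For categorical variables, participants with missing data are not included in calculations of percentages unless otherwise specified". Sections 2.4.3, 2.5.2 and 2.5.4 make no exception for this endpoint.

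On disclosure, section 1.5 is marked not applicable. Section 1.6 states that, because of the termination, the protocol's efficacy evaluations lost their relevance and were not done. Section 2.4 adds that primary and secondary efficacy data are summarised descriptively.

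**The concern.** The same endpoint appears in both documents under the same ITT label, with opposite treatment of missing values. Under the protocol the denominator is everyone randomised to the arm. Under the SAP default it is those with a usable HbA1c. The observed-case statement in SAP 2.4 is worded for quantitative endpoints, so a yes/no endpoint does not obviously fall under it. No sentence in SAP 1.6 says that the nonresponder rule has gone.

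A reader who knew the protocol could therefore take the percentage as a share of all randomised participants. The SAP figure can never be lower than the protocol-rule figure. If missingness differs between arms, the apparent gap between a dose and placebo could also move in either direction.

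**Working it through.** **The plan's own figure.** Neither document states a responder rate, a missing rate or a power for this endpoint. The power figures in protocol 9.2 and SAP 1.3 concern mean HbA1c change and do not bear on this point.

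**The denominator.** Let N be the number randomised to an arm, k the number with a usable HbA1c, r the number below 7%, and m = 1 − k/N the share missing.

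- SAP default: p = r/k.
- Protocol rule: r/N = p × (1 − m).
- Difference within an arm: p × m.

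The numerator r is the same under both rules.

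**Illustration.** Take N = 100, the planned arm size, and assume p = 40%. The missing numbers are also assumptions.

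| Missing | Usable | Responders | SAP default | Protocol rule |
|---|---|---|---|---|
| 10 | 90 | 36 | 36/90 = 40% | 36/100 = 36% |
| 20 | 80 | 32 | 32/80 = 40% | 32/100 = 32% |
| 60 | 40 | 16 | 16/40 = 40% | 16/100 = 16% |

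**Gap between arms.** With equal missingness the protocol-rule gap is (1 − m) times the observed gap. An assumed 25-point gap becomes 0.9 × 25 = 22.5 points at 10% missing and 0.8 × 25 = 20 points at 20%. With unequal missingness it can move either way. If both arms show 40% but the active arm has 30% missing and placebo 10%, the rule gives 0.4 × 0.7 = 28% against 0.4 × 0.9 = 36%, a gap of −8 points. Swapping the missing shares gives +8.

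**What these differences measure.** They compare the SAP figure with a rule that treats every missing value as failure. That rule was written for a trial expected to run its course. Here m includes people whose Week 30 or Week 56 visit never came because the sponsor stopped the study. In the last row, if most of the 60 were cut off in this way, the 16% would mainly describe when people were enrolled. The differences are therefore not the size of an error in the SAP figure.

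**Week 56.** SAP 2.4.3 gives two presentations and says who is in each. The first is described as: "Including all Week 56 visits performed per protocol as well as premature end of treatment/study visit recorded as Week 56 due to early termination". Visits at termination thus supply values for that presentation. The second is confined to those who completed treatment and/or study. Neither is offered as a rate among everyone randomised, so the question is mainly one about Week 30.

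**Could the nonresponder rule be kept for part of the trial?** One could apply it only to participants whose ±30-day window had closed by 09 September 2020. For Week 30 the window closes on Day 210 + 30 = 240, so Day 1 must fall on or before 14 January 2020 (239 days earlier). For Week 56 it closes on Day 392 + 30 = 422, so Day 1 must fall on or before 16 July 2019 (421 days earlier). This does not isolate the termination cleanly. SAP 2.5.4 takes scheduled endpoint visits as they were collected, and the ±30 days limit only substitute unscheduled measurements. A late Week 30 visit pre-empted by the termination could still be missing because of it. The Week 56 subset may also be empty.

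**The case for a change.** The strongest case for a change is that the protocol wrote a rule for this one endpoint, and a general default in the SAP reverses it without saying so. SAP 1.6 reports that efficacy evaluations were dropped, not that one survives under the opposite rule. Section 2.5.3 warns only in general terms that some participants may be absent, and promises the number missing only when relevant. The disposition table uses all randomised participants as its denominator, which could lead a reader to assume the same here. Naming the departure would take two sentences.

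Part of this stands: the specific switch is not named, and naming it would do no harm. The rest is weaker. The nonresponder rule belonged to a stratified comparison that SAP 1.6 covers when it drops the protocol's efficacy evaluations. Section 2.4.3 promises observed values for a list that includes this percentage. Read with 2.5.3, that leaves an analyst one way to compute it. The entry in section 1.5 is no evidence of concealment, since by its title that section concerns changes to the protocol's statistical text, while SAP changes belong in 1.6, which is filled in. Finally, the endpoint is itself a count, so a reader with r and N can form the protocol-rule percentage directly.

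**Conclusion.** No change to the plan follows. The two documents do differ in the denominator, and the SAP announces the change only in general terms. But observed-case reporting is a fair choice once the sponsor has stopped the trial, the governing rule is written in SAP 2.5.3, and a further sentence would restate it. A nonresponder table in a calendar-defined subset is a matter of preference and would change no conclusion.

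Within an arm the size is the observed rate times the share missing. Its value is unknown because the documents give neither quantity. The effect on the gap between arms has no fixed direction.

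This view rests on two assumptions. The first is that the synopsis report shows the responder count with the number assessed or the arm size, as is usual for an endpoint defined as a number of participants. The second is that the percentage stays descriptive, as SAP 1.6 and 2.4 intend. If it were later used to claim an advantage over placebo, the denominator and the reasons for missing values would need to be set out beside it.
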